11.7.4 Electrocardiogram Analyses

A shift table will be provided for ECG evaluation between baseline and Visit 10.

11.7.5 Physical Finding Analyses

Summary statistics will be calculated for measured values and changes from baseline in body weight at each scheduled visit. For the evaluation of edema, the results (presence

or absence) will be tabulated for each expression site.

11.7.6 Columbia-Suicide Severity Rating Scale

The data collected from C-SSRS will be tabulated.

11.7.7 Hospital Anxiety and Depression Scale

The subscales of anxiety and depression for HADS will be summarized at each scheduled visit.

11.7.8 Other Safety Analyses

The data collected from the ophthalmologic examination will be tabulated at each scheduled visit.

11.8 Other Analyses

Not applicable.

11.9 Data Safety Monitoring Board

An independent DSMB will be responsible for reviewing unblinded safety data in an ongoing manner and for monitoring and assuring overall safety of the study subjects. In accordance with an agreed-upon charter, the DSMB will meet periodically, on a regular and/or ad hoc basis, to discuss and address any emerging safety or tolerability issues, including SAEs, discontinuations due to AEs, etc, as well as other relevant study information, such as recruitment status, ineligibility rates, and data quality. Based on any formal DSMB review meeting where blinded or unblinded safety data are reviewed and discussed, the DSMB will recommend to the sponsor one of the following:

- Continue the study without modification
- Continue the study but modify the protocol and/or ICF
- Suspend the study (or a cohort) until further notice, with recommendations for further action to address specific issues and appropriately managing active study subjects
- Terminate the study (or a cohort) with provisions for orderly discontinuation in accordance with GCP.

Modification, suspension or termination may be made for any of the following reasons:

- Concern about drug-induced liver injury
- Concern about suicide

- Any other safety concern

The approach to study (or cohort) modification, suspension, or termination will be described in the DSMB charter.

The sponsor (Head of Clinical Safety and Pharmacovigilance) will be notified of the DSMB decision by the DSMB chairman within 3 days after the meeting. Minutes of all formal DSMB meetings and discussions will be maintained by the independent statistician, in a secure location, until completion or termination of the study, at which point they will be forwarded to Daiichi Sankyo for archiving.

11.10 Hepatic Adjudication Committee

The HAC will comprise at least two qualified hepatologists, who are not investigators in the study and not otherwise directly associated with the sponsor. The HAC will follow its own charter for processing and adjudicating hepatic events. The HAC will adjudicate hepatic events in a blinded manner. This adjudication will be independent of the investigators. The HAC will complete assessments on an ongoing basis.

Adjudication of hepatic events will be based on evaluation of eCRFs and source documents, as available, including but not limited to hospital discharge summaries, diagnostic imaging, histopathology, consultation, and laboratory reports. Such patient's relevant records will be provided to the HAC from the study sites according to HAC request.

11.11 Sample Size Determination

Approximately 750 subjects will be randomized to one of placebo (300 subjects), DS-5565 15 mg QD (150 subjects), DS-5565 10 mg BID (150 subjects), or DS-5565 15 mg BID (150 subjects) according to the randomization ratio of 2:1:1:1.

This sample size provides around 90% statistical power which is the probability of DS-5565 15 mg BID (or DS-5565 10 mg BID) superiority over the placebo under the assumption of 0.6 difference (vs placebo) in change from baseline in ADPS (Δ ADPS) for all DS-5565 arms and common SD for Δ ADPS of 1.8 units. The statistical power is based on Analysis of Variance (ANOVA) using combination approach of Bonferroni-Holm method and gate-keeping procedure (see Section 11.5.1) to control the type I error rate at less than 0.05. The statistical power shown in Table 11-1 is simulation-basis (100,000 repetitions).

Table 11-1 Statistical powers (%) of DS-5565 15 mg QD, 10 mg BID, and 15 mg BID being superior over placebo

Difference (15 mg QD, 10 mg BID, 15 mg BID) and SD	15 mg QD	10 mg BID	15 mg BID
Diff=(0.6, 0.6, 0.6), SD=1.8	87.0%	89.5%	89.3%
Diff=(0.4, 0.6, 0.6), SD=1.8	56.9%	87.7%	87.5%

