11.2 General Statistical Considerations

The statistical package SAS[®] (Version 9.2 or higher) will be used to produce tables, figures, and listings.

The modified intent-to-treat (mITT) analysis set will be used as a primary efficacy analysis set for all efficacy analyses and the per-protocol set (PPS) will be used for sensitivity analysis. All safety analyses and pharmacokinetic analyses will be conducted for the safety analysis set and PK analysis set, respectively.

The primary imputation will be based on “nonfuture dependence” model using the pattern mixture approach under the missing not at random (MNAR) mechanism for the missing weekly ADPS data¹⁹⁻²¹. Reason for dropout together with the time of dropout will be used for constructing the missing data pattern. Detail will be at Section 11.5.1 and in the SAP.

Raw data will be presented to the exact precision at which they were collected.

For summary statistics, means and medians will be displayed to one more decimal place than was determined for raw data, dispersion statistics will have two more decimal places, and the minimum and maximum will be displayed to the same number of decimal places as the raw data.

Quantitative data will be tabulated with descriptive summary statistics: arithmetic mean, standard deviation (SD), median, minimum and maximum values, and number of observations. For categorical data, frequency tables will be provided.

All hypothesis testing will provide the *P* values and their corresponding two-sided 95% confidence intervals if applicable. The significance level is 0.05 (two-sided) for all hypothesis testing. The type I error rate will be controlled at less than 0.05 for the multiple comparisons of the primary endpoint of ADPS at Week 14 between each DS-5565 arm (15 mg QD, 10 mg BID, or 15 mg BID) and placebo, using combination approach of Bonferroni-Holm method and gate-keeping procedure (see Section 11.5.1). No adjustment for multiple comparisons will be made for the secondary efficacy analyses.

Analysis for the change from baseline, including the shift table, will be conducted for the

subjects who have an available baseline value and at least one post-randomization value. Subgroup analyses by country (eg, Japan, Korea, and Taiwan) will be conducted for some of efficacy and safety analyses specified in the SAP.

PK analysis will be detailed in the PK analysis plan (PAP).

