The primary imputation will be based on “nonfuture dependence” model¹⁹⁻²¹ using the pattern mixture approach with shifting parameters under the MNAR mechanism for the missing weekly ADPS data. Reason for dropout together with the time of dropout will be used for constructing the missing data pattern. The statistical model used for the MI data generation will be the Markov Chain Monte Carlo (MCMC) method with adjustment for covariates (eg, treatment group, age, sex) to produce a monotone pattern first, and then the imputation will continue using the Regression with Predictive Mean Matching (REGPMM) method for the monotone pattern with the same set of covariates. The imputed value will be set as 10 (the maximal ADPS score) when the imputed value of ADPS score is over 10. Additionally, for dropouts due to LOE, the imputed values will be bound so that a subject’s imputed weekly ADPS after discontinuation cannot be better than that subject’s baseline ADPS. Each complete imputed dataset will be analyzed using the MMRM with treatment, week, treatment-by-week as the fixed effects, week as the repeated measure, and baseline ADPS as the covariate. The results of MMRM analysis from each complete imputed dataset will be combined using Rubin’s rule. All reasons for discontinuation will be categorized, to the extent possible, into either LOE or AE based on detail specified in the Case Report Form. Only reasons that cannot be classified into the above two categories will be considered as “all other reasons (AOR)”. The primary shifting parameter values corresponding to the three categories in the pattern mixture model (PMM) will be chosen as (1.0, 1.0, 0.5) for dropouts due to AE, LOE and AOR, respectively, and the corresponding shifting amount of the weekly ADPS imputed at first missing week is given by $(1.0, 1.0, 0.5) * RSD * U(0,1)$ where $U(0,1)$ is a random variable from a uniform distribution with a range of 0 to 1, and RSD is the residual standard deviation at first missing week after imputation.

The type I error rate will be controlled at less than 0.05 for the multiple comparisons of the primary efficacy analyses in the following multiple test procedure.

- 1) DS-5565 10 mg BID and 15 mg BID will be tested against placebo using Bonferroni-Holm method at significance level of 0.05.
- 2) The following statistical test will be performed according to the result of 1).
 - If both of arms are statistically significant, DS-5565 15 mg QD arm will be

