tested at level of 0.05.

- If neither of the arms is statistically significant, DS-5565 15 mg QD arm will not be tested.
- If either DS-5565 10 mg BID or DS-5565 15 mg BID is statistically significant, DS-5565 15 mg QD arm will be tested at level of 0.025.

Sensitivity analyses will include following:

- The above primary “nonfuture dependence” MNAR model with different shift parameters including (0, 0, 0)
- Placebo multiple imputation^{17,18}
- MMRM using observed data only
- ANCOVA using BOCF
- ANCOVA using LOCF
- The above primary “nonfuture dependence” MNAR model with the same shift parameters as the primary analysis (i.e., (1.0, 1.0, 0.5) using PPS).

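### Table 11-1 cannot come from the test procedure in Section 11.5.1: power for the BID doses falls when only the QD effect is changed

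*Combined protocol and SAP*

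**What the plan says.** Section 11.5.1 of the double-blind protocol sets a two-step procedure. Step 1: "DS-5565 10 mg BID and 15 mg BID will be tested against placebo using Bonferroni-Holm method at significance level of 0.05". Step 2 is introduced with "The following statistical test will be performed according to the result of 1") and concerns 15 mg QD alone. QD is tested at 0.05 if both BID doses are significant and is not tested if neither is. If exactly one is, "DS-5565 15 mg QD arm will be tested at level of 0.025". No step returns to a BID dose after QD has been tested. Section 11.2 adds "The significance level is 0.05 (two-sided) for all hypothesis testing" and points to Section 11.5.1 for the multiplicity rule.

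Section 11.11 plans 300 placebo subjects and 150 in each DS-5565 arm, "according to the randomization ratio of 2:1:1:1". On power it says: "The statistical power is based on Analysis of Variance (ANOVA) using combination approach of Bonferroni-Holm method and gate-keeping procedure (see Section 11.5.1"). The powers are simulated with 100,000 repetitions. Table 11-1 has two rows. The first assumes a difference of 0.6 in every arm. The second is "Diff=(0.4, 0.6, 0.6), SD=1.8", in the order QD, 10 mg BID, 15 mg BID, so it changes the QD effect and nothing else.

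**The concern.** Under the written rule the two BID decisions are functions of the two BID p values only. With a pooled ANOVA error, which is a within-arm quantity, the joint distribution of those p values does not involve the QD mean. The BID columns should therefore be identical in the two rows. In the table each falls by 1.8 points.

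If the table was produced by another procedure, the power statement behind the sample size describes a test that the protocol does not specify. Error control is also at stake. The protocol promises a type I error below 0.05, and two procedures with different power may differ in whether they keep that promise.

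**Working it through.** **Inputs.** n = 300/150/150/150, differences 0.6 or 0.4, SD 1.8 and 100,000 repetitions (Section 11.11); two-sided 0.05 (Section 11.2); decision rule (Section 11.5.1). Pooled error has 750 − 4 = 746 df. No dropout allowance is stated and none was used.

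**Single comparisons.** SE = 1.8 × √(1/300 + 1/150) = 1.8 × 0.1 = 0.18.
- Difference 0.6: 0.6/0.18 = 3.33, giving power of 91.5% at 0.05 and 86.3% at 0.025.
- Difference 0.4: 0.4/0.18 = 2.22, giving 60.3% and 49.2%.

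Holm power for one BID dose must lie between 86.3% and 91.5%.

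**Is the drop noise?** The Monte Carlo SE at 90% is √(0.9 × 0.1/100,000) = 0.095 point. For the difference between two independent rows it is √(0.895 × 0.105/100,000 + 0.877 × 0.123/100,000) = 0.142 point. The fall of 1.8 points is 1.8/0.142 = 12.7 SEs, and it appears in both BID columns.

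**Attempt to reproduce the table.** Simulation with 1,000,000 repetitions, pooled-variance t tests, and rejections counted only in favour of DS-5565. Power (%) is given as QD / 10 mg BID / 15 mg BID.

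| Procedure | Row 1 (0.6, 0.6, 0.6) | Row 2 (0.4, 0.6, 0.6) |
|---|---|---|
| Table 11-1 as stated | 87.0 / 89.5 / 89.3 | 56.9 / 87.7 / 87.5 |
| Section 11.5.1 as written | 87.6 / 90.2 / 90.2 | 57.9 / 90.2 / 90.2 |
| Loop-back rule (below) | 87.0 / 89.4 / 89.4 | 56.9 / 87.6 / 87.6 |
| Holm over all three doses | 89.0 / 89.0 / 89.0 | 57.4 / 86.8 / 86.8 |
| BID doses fixed at 0.025, same QD gate | 87.0 / 86.1 / 86.1 | 57.0 / 86.1 / 86.1 |
| Holm, QD only after both BID doses | 78.9 / 90.2 / 90.2 | 54.4 / 90.2 / 90.2 |

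Loop-back rule: each BID dose is tested at 0.025. QD is then tested at 0.025 if one BID dose is rejected, or at 0.05 if both are. The remaining BID dose is tested at 0.05 only once QD has been rejected.

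The BID figures can be checked by hand. Both BID doses have the same effect, so each one's power is half of P(at least one rejected) + P(both rejected).
- Written rule: (96.09 + 84.29)/2 = 90.2 in both rows.
- Loop-back rule: (96.09 + 82.64)/2 = 89.4 in row 1 and (96.09 + 79.07)/2 = 87.6 in row 2.

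The gaps between the written rule and the table are 0.6, 0.7 and 0.9 point in row 1, and 1.0, 2.5 and 2.7 points in row 2. Other readings do not close them. Two-sample t tests give BID 90.1% in both rows. An overall F-test gate, which Section 11.5.1 does not contain, gives 89.8% then 89.1%.

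**Familywise error.** Suppose one BID dose works, and the other BID dose and QD are null. After the first rejection, Holm tests the null BID dose at the full 0.05, while QD is also tested at 0.025 or more. The two null tests can together spend up to 0.05 + 0.025 = 0.075. Simulated error, counting two-sided rejections:

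| Effect of the active BID dose | Written rule | Loop-back rule |
|---|---|---|
| 3.0 (assumed, to show the limit) | 0.072 | 0.048 |
| 0.6 (the protocol's own value) | 0.063 | 0.043 |

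**The case against.** The mismatch does not damage the design. Section 11.11 claims only around 90% power for a BID dose at a difference of 0.6, and the written rule delivers 90.2%. The BID entries in the table therefore err on the conservative side, and the largest gaps are confined to the secondary scenario. The primary hypothesis in Section 2.2 needs only one BID dose to succeed. That probability is 96.1% in both rows under either rule. The ANOVA calculation is in any case a simplification of the planned multiple imputation with MMRM, so a point or two matters little. No section describes a loop-back step, so saying that it was simulated is an inference from fit. The loop-back rule would also let a primary BID result depend on the secondary QD dose.

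Most of this stands. The sample size is not shown to be too small, the attribution is an inference, and loop-back is one option among several. It does not rescue the table, whose figures are attributed to a procedure that cannot generate them. The simplification to ANOVA does not explain the gap either, because the drop is impossible for the written rule within that same ANOVA framework.

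**Conclusion.** Table 11-1 is wrong as a description of Section 11.5.1. That conclusion is logical and needs no simulation: the written rule makes BID power independent of the QD effect, and the table does not. The error is at most 2.7 points (87.5% stated against 90.2%), and it understates BID power. These figures assume normal data, SD 1.8, the planned arm sizes with no dropout, and pooled error.

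That a loop-back rule was simulated is probable, since it alone among the procedures tried matches all six cells within 0.2 point, but the documents do not say so. The practical consequence is that the stated powers and the rule to be applied belong to different procedures. The written one exceeds the promised 0.05 when a single BID dose is effective, reaching 0.063 at the protocol's own effect of 0.6 and 0.072 in the limiting case.

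**What to change.** State one procedure that controls the familywise error, and have Section 11.5.1 and Table 11-1 both describe it. There are two ways:

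- Rewrite Section 11.5.1 as the loop-back rule that fits the table, and keep the figures once the original simulation code confirms that this is what was run. This is the least work. The sponsor should accept openly that the second BID dose may then depend on the QD result.
- Adopt another controlling rule, rerun Table 11-1 and restate the powers. Holm with QD tested only after both BID doses, for example, keeps BID power at 90.2% in both rows and lowers QD power to 78.9% and 54.4%.

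Rerunning the table under the present wording would correct the figures but leave the error inflation in place. The cost is a change of wording or a short simulation, to be settled before unblinding. The sample size stays at 750.

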12. DATA INTEGRITY AND QUALITY ASSURANCE

The investigator/study site will permit study-related monitoring, audits, IRB/independent ethics committee (EC) review, and regulatory inspections by providing direct access to source data/documents. Direct access includes permission to examine, analyze, verify, and reproduce any records and reports that are important to the evaluation of a clinical study.

12.1 Monitoring and Inspections

The monitor and regulatory authority inspectors are responsible for contacting and visiting the investigator for the purpose of inspecting the facilities and, upon request, inspecting the various records of the study (eg, CRFs, source data, and other pertinent documents).

The monitor is responsible for visiting study site(s) at regular intervals throughout the study to verify adherence to the protocol; completeness, accuracy, and consistency of the data; and adherence to International Conference on Harmonization (ICH) GCP and local regulations on the conduct of clinical research. The monitor is responsible for inspecting the CRFs and ensuring completeness of the essential study documents. The monitor should have access to subject medical records and other study-related records needed to verify the entries in the CRFs.

The monitor will communicate deviations from the protocol, standard procedures, GCP, and applicable regulations to the investigator and will ensure that appropriate action designed to prevent recurrence of the detected deviations is taken and documented.

The investigator agrees to cooperate with the monitor to ensure that any problems detected in the course of these monitoring visits are addressed and documented.

In accordance with ICH GCP and the sponsor's audit plans, this study may be selected for audit by representatives from the sponsor. Inspection of site facilities (eg, pharmacy, drug storage areas, laboratories, etc.) and review of study-related records will be performed in order to evaluate the conducting of the study and compliance with the protocol, ICH GCP, and applicable regulatory requirements.

12.2 Data Collection

12.2.1 Style of Data Collection

12.2.1.1 Case Report Form

This study will use an Electronic Data Capture (EDC) system (Table 12-1) to generate CRFs, so the CRFs will be entered electronically. CRFs (including audit trails) will be prepared for each subject. The eCRF will be completed, reviewed, and e-signed by the investigators. The EDC system will be validated prior to use.

Table 12-1 Electronic Data Capture System

Name of EDC system	Medidata Rave®
EDC system developer	Medidata Solutions Inc.
Entry method	Web-based data entry
Input terminal	Desktop computer at the study site
Incompatible operating systems	None
Recommended browsers	The Medidata Rave® supports any browser which is HTML 4, HTML 5, and CSS2 compliant. Browsers must have JavaScript enabled.
Screen Resolution	The minimum screen resolution required to properly display Medidata Rave applications is 1024 x 764.
Connection Speed	128kbps is the minimum connection speed recommended for using Medidata Rave.
Other	Adobe Flash Player : ver. 10 or above is required

12.2.1.2 Electronic Daily Diary

This study will use an Electronic Patient Report Outcome (ePRO) system (Table 12-2) to collect patient daily diary data. The device for electronic daily diaries (including audit trails) will be prepared for each subject. The electronic daily diaries will be completed by the patient and reviewed by the investigators. The ePRO system will be validated prior to use.

Table 12-2 Electronic Patient Report Outcome System

EDC system developer	eResearchTechnology, Inc
Entry method	Patient-reported outcomes; Hand-held device
Input terminal	DIARYpro® Mobile
Incompatible operating systems	None
Recommended browsers	DIARYpro® Mobile is a proprietary system that runs on a Windows platform. Windows OS and Internet Explorer 7.0, 8.0 or 9.0
Screen Resolution	N/A, as software is programmed to fit on the DIARYpro mobile device.

12.2.1.3 Other Reports

Results of pharmacokinetic test and laboratory tests are reported by central laboratory, separately. Procedure for these reports are set separately.

12.2.2 Preparation of Case Report Forms and Daily Diaries

All persons who make entries and/or corrections on CRFs or daily diaries should be trained and should be assigned their own accounts to use the EDC or ePRO system. The training record is regarded as a signature sheet.

- 1) CRFs will be created for subjects who sign the ICF for the study, and electronic daily diaries will be created for subjects who are conducted screening visit for the study.
- 2) The investigator or sub-investigator will prepare the CRF in accordance with CRF completion guidelines that are provided by the sponsor.
- 3) If study staff assists in the preparation of the CRF, they will do so under the direction of the investigator or sub-investigator.
- 4) The investigator will submit the CRF to the sponsor, and will keep a copy.
- 5) If there is a contradiction between some of the data that is entered in the CRF and the source documents, the investigator will prepare a separate record that explains the reason(s) for this discrepancy, and will submit that record to the sponsor.
- 6) Subject will receive the device for the electronic daily diaries and answer to the question.
- 7) The device for the electronic daily diaries should be collected when subject terminate the study.

12.2.3 Signatures or Seals on the Case Report Form

The investigator will confirm all of the CRFs that are prepared at that study site, and will enter his or her electronic signature in the file.

The investigator will also confirm all of the electronic daily diaries that are prepared at that study site.

12.2.4 Data Correction

- 1) The investigator, sub-investigator, or study staff will correct the data in the CRF in accordance with the CRF completion guidelines that are provided by the sponsor.
- 2) The investigator will be responsible for the content of entries in the CRF.
- 3) Procedure for data correction of the electronic daily diariys will set separately.

